**Responders according to SGRQ Total Score**

- A participant will be considered as a responder according to SGRQ total score if their change from baseline SGRQ total score  $\leq -4.0$ .
- A participant will be considered as a non-responder according to SGRQ total score if their change from baseline SGRQ total score  $>-4.0$ .
- If SGRQ total score is missing at a visit, the response status will be missing at that visit.
- Change from baseline SGRQ total score will be rounded to 1dp prior to assigning responder status.

**Rescue Use via Sensor**

**Mean Number of Occasions and Percentage Rescue Free Days via Sensor**

- The mean number of occasions of rescue per day and the percentage of rescue-free days will be calculated over the same time periods and using the same assumptions as rescue use via diary.
- Rescue-free Days - days within the diary data collection period with no recorded rescue inhaler usage by the sensor will be assigned a rescue inhaler usage of 0.

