7.1.1. Medical Devices

- Subject to availability and any local restrictions on use, MDI sensor devices (manufactured by and purchased from Propeller Health) are being provided by GSK for this study. These devices are fitted onto rescue medication MDI devices to electronically record rescue medication usage. The MDI sensor devices have US FDA 510(k) clearance to market (Class II medical device) and European Union CE marking (Class I medical device).
- Subject to availability and any local restrictions on use, ActiGraph GT9X physical activity monitors (manufactured by and purchased from ActiGraph, LLC) are being provided by GSK for the subset of participants that will be included in the physical activity monitoring subgroup. The device is a tri-axial accelerometer. The participant wears the devices for the period of time that physical activity is being monitored.
- Additional descriptive information and instructions for the eMDI and physical activity monitoring devices are provided in the SRM.
- GSK medical device incidents, including those resulting from malfunctions of the device, must be detected, documented, and reported by the Investigator throughout the study (see Section 9.2).

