### 5.2. Baseline Definitions

Any assessments made after the start of study treatment will not be included in the derivation of baseline. Assessments made on the same day as the start of treatment are assumed to be taken prior to first dose.

If baseline data are missing, no derivation will be performed and baseline will be set to missing.

Parameter	Baseline Used in Data Display
E-RS: COPD total and subscale scores	Mean score during a stable period between (Latest of (7 days before Study treatment start date (Day 1) and day of Visit 1 (Screening)) and day before Day 1 of study treatment. Data must be present on at least 4 days
EXACT (for determining EXACT events)	Defined according to the EXACT User Manual v8.0 ( Evidera, 2016a )
SGRQ total and domain scores	Day 1
CAT score	Day 1
Rescue use (diary card and sensor data, mean number of puffs/occasions per day and percentage of rescue-free days)	Mean score during a stable period between (Latest of (7 days before Study treatment start date (Day 1) and day of Visit 1 (Screening)) and day before Day 1 of study treatment. Data must be present on at least 4 days.
PROactive score	A PROactive Total Score and two domain scores (amount and difficulty) will be derived using data from the C-PPAC questionnaire on Day 1 and physical activity

Parameter	Baseline Used in Data Display
	monitor worn between Visit 2 and Visit 3 (7 days). The activity monitor must have been worn for at least 3 days with $\geq 8$ hours wearing (the 3 days do not need to be consecutive). Further details of the derivation are described in Section 14.6.3 and in the IMI PROactive user manual (14JUN16).
Blood pressure (BP)	Latest pre-dose assessment with a non-missing value for both systolic and diastolic BP, including those from unscheduled visits
Pulse rate, laboratory data, ECG	Latest pre-dose assessment with a non-missing value for the individual assessment, including those from unscheduled visits
Post-bronchodilator (BD) FEV1, post-BD FVC	Day 1

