#### 7.2.5. Rescue Use

The monthly mean number of puffs of rescue use per day according to diary card data and the monthly mean number of occasions of rescue use per day according to sensor data and the monthly percentage of rescue-free days according to diary card data and according to sensor data will be analysed using the same methodology as for E-RS: COPD total and subscale scores longitudinal analysis (as described in Section 7.1.3.5.2). A figure of daily mean number of puffs of rescue medication per day using diary data over time and daily mean number of occasions of rescue medication per day using sensor data over time will be generated for the PP population.

Additional analysis of rescue use according to sensor data may be performed and will be defined in a separate RAP.

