Month 3 	Study day 57	Study day 84																						
Month 4 	Study day 85	Study day 112																						
Month 5 	Study day 113	Study day 140																						
Month 6 	Study day 141	Earliest of (Study day 168 and day before study treatment stop date)																						
[1] The denominator for baseline and monthly mean scores is the number of days with a non-missing score; this is also used to determine whether or not a baseline (≥4 days) or monthly mean (≥10 days) is calculated.																								
EXACT PRO																								

 
• The EXACT-PRO (Evidera, 2016a) is a 14-item daily diary (typically completed at bedtime)
 
• The daily E-RS: COPD total score (and subscales) will be computed according to the E-RS in COPD user manual (Evidera, 2016b).
 
• The monthly mean for E-RS: COPD total score, and the subscale scores RS-Breathlessness, RS-Cough and Sputum, and RS-Chest Symptoms will be calculated as the mean of the daily scores in the monthly intervals defined above.
 
• Mean monthly score = (sum of daily scores/# diary days completed).
 
• A participant must have at least 10 days of diary data in any month to contribute a non-missing monthly mean of daily values; otherwise the monthly mean for that month will be considered missing.
 
• A participant must have at least 4 days of diary data in the 7 days prior to treatment start date to contribute a non-missing mean of daily values for baseline; otherwise baseline will be considered missing.
 
• If missing values occur for individual items, the E-RS: COPD total score and E-RS: COPD subscale
 
																								

Daily eDiary endpoints
 
score that contain the item will be set to missing on that day.

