
Season
 
 
• For each participant and each month, season will be assigned based on the first date with a non-missing daily score in the monthly mean E-RS: COPD total score.
 
• Australia will add 6 months to the first day of the monthly mean E-RS: COPD total score before season is assigned.
 
• If the month of the first day of the monthly mean score period is:             
 
▪ Dec, Jan or Feb then season is Winter
 
▪ Mar, Apr or May then season is Spring
 
▪ Jun, Jul or Aug then season is Summer
 
▪ Sep, Oct or Nov then season is Fall
 
 
 

Mean Number of Rescue Puffs per Day and Percentage Rescue Free Days
 
 
• If a participant has more than one daily diary record for any given day, the worst case response on that day for each endpoint will be used in the summaries and analyses. i.e. the maximum number of puffs of rescue use reported will be counted for the day in question and used to determine if it was a rescue-free day.
 
• A rescue-free day is defined as a day where the total puffs is 0.
 
• For each summary period, the mean number of puffs per day and the percentage of rescue free days, will be calculated, using the number of days with non-missing values for the endpoint as denominator.
 
• Rescue use will be summarized over the periods defined above.
 

HCRU Exacerbations
Duration

 
The duration of the exacerbation will be calculated as (exacerbation resolution date or date of death - exacerbation onset date + 1).
 

Severity

 
Each HCRU exacerbation will be categorized based on severity as follows:                             
 
Mild: no treatment with oral/systemic corticosteroids and/or antibiotics and not involving hospitalisation, an emergency room visit or resulting in death
 
Moderate: required treatment with oral/systemic corticosteroids and/or antibiotics (not involving hospitalisation, an emergency room visit or resulting in death).
 
Severe: required in-patient hospitalization, an emergency room visit, or resulted in death
 
 
 

Time to First Exacerbation

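### Sensor rescue use: a day with no sensor record is scored as zero use with no check that the sensor was working, so sensor failure after randomization counts as rescue-free

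*SAP*

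**What the plan says.** SAP 14.6.3 (Rescue Use via Sensor) derives two quantities: mean occasions of use per day and percentage of rescue-free days. Its rule for a blank day is that days in the diary collection period "with no recorded rescue inhaler usage by the sensor will be assigned a rescue inhaler usage of 0". It does not require that the sensor was attached, powered or transmitting. In other respects the two quantities "will be calculated over the same time periods and using the same assumptions as rescue use via diary".

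The diary rules adopted in this way treat a blank differently. Diary rescue summaries are formed "using the number of days with non-missing values for the endpoint as denominator". The footnote to the period table in the same section says "The denominator for baseline and monthly mean scores is the number of days with a non-missing score". It uses that same count to decide whether a baseline value (4 days or more) or a monthly value (10 days or more) exists. SAP 5.2 repeats the baseline condition for diary and sensor rescue use: "Data must be present on at least 4 days".

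SAP 7.2.5 sends "the monthly mean number of occasions of rescue use per day according to sensor data", and the sensor rescue-free percentage, to the frequentist MMRM used for E-RS:COPD. The outputs are final-analysis tables 2.40 to 2.45 and figures 2.30 to 2.32, in the Per Protocol population.

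On supply, Protocol 7.1.1 makes provision conditional: "Subject to availability and any local restrictions on use, MDI sensor devices" are provided by the sponsor. Protocol 6.5 nevertheless makes electronic capture by the sensor part of a successful run-in, without stating how many sensor days are needed.

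**The concern.** A sensor reports actuations, so silence has two meanings: the inhaler was not used, or the device was not recording. The rule gives both the value 0. For the diary, a blank is unknown and drops out. For the sensor, a blank becomes an observed good day.

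Non-recording is foreseeable from the protocol. The schedule of activities lists sensor dispensing only at Visit 2, ahead of 24 weeks of treatment. The sensors are fitted to rescue inhalers that the sponsor does not supply (Protocol 7.1.1 and 7.7), so a replacement or second inhaler could carry no sensor. Protocol 9.2.8 provides for device malfunctions. For the trial's other device, SAP 14.6.3 accepts activity-monitor data only on days with enough wear time. The rescue sensor has no counterpart to that check.

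At stake is the sensor version of a secondary endpoint. Because run-in success needs sensor capture, sensors probably work at baseline. Later failures would then look like improvement in every arm, including in the daily plot from Day -7 to Day 168 (figure 2.30).

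**Working it through.** The plan gives no expected value, failure rate or power for the sensor endpoints, so there is no figure to reproduce. The check applies the SAP rule in closed form.

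**Inputs from the documents:** a 28-day month; zero for a blank sensor day; a minimum of 10 non-missing days per month (SAP 14.6.3).

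**Assumed inputs (not in the documents):** true use of 2 occasions per day; true rescue-free share p = 40%, with a range of 10 to 60%; share of days on which the sensor does not record q = 10, 20 or 30%.

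**Can the 10-day rule remove a dead-sensor month?** The percentage of rescue-free days divides by non-missing days. Unless the device transmits explicit zero records, which the documents do not say, assigned zeros must sit in that denominator or no rescue-free day could be counted. The same count drives the 10-day rule. On this reading all 28 days are always present.

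**One participant-month with k working days.** Recorded mean = 2 × k/28. Recorded rescue-free share = (0.40 × k + 28 − k)/28.

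| Working days | Mean under SAP rule | Rescue-free under SAP rule | If non-recording days were missing |
|---|---|---|---|
| 28 | 2.00 | 40.0% | 2.00, 40% |
| 20 | 40/28 = 1.43 | 16/28 = 57.1% | 2.00, 40% |
| 10 | 20/28 = 0.71 | 22/28 = 78.6% | 2.00, 40% |
| 9 | 18/28 = 0.64 | 22.6/28 = 80.7% | month missing |
| 0 | 0.00 | 28/28 = 100% | month missing |

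**Group level.** Recorded rescue-free share = p + q(1 − p); recorded mean = 2(1 − q).

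- p = 40%, q = 10/20/30%: 46/52/58% rescue-free; mean 1.80/1.60/1.40.
- Range over p: at q = 10%, a true 10% reads 19% and a true 60% reads 64%; at q = 30%, they read 37% and 72%.

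**Change from baseline with no true change, sensor working at baseline.** The spurious change is −2q = −0.2/−0.4/−0.6 occasions per day and q(1 − p) = +6/+12/+18 percentage points.

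**Treatment difference, equal q in both arms.** The true difference is multiplied by (1 − q). A true −0.5 occasions per day becomes −0.45/−0.40/−0.35, and a true +10 points becomes +9/+8/+7.

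**Treatment difference, unequal q, no true effect.** With 5% loss on placebo and 10/15/20% on active, the spurious difference is −2 × (0.05/0.10/0.15) = −0.1/−0.2/−0.3 occasions per day and 0.60 × (0.05/0.10/0.15) = +3/+6/+9 points. Reversing the arms reverses the sign.

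**The case against.** Several points limit the concern.

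- **Never-issued sensors.** A reader might infer that a participant who never received a sensor scores 100% rescue-free throughout. The documents do not support this as a general result. Under Protocol 6.5 a participant without sensor capture should be a run-in failure and not be randomized. SAP 5.2 also asks for baseline data on 4 days, and without a baseline there is no change to analyse. If zeros filled the baseline too, the change would be 100% − 100% = 0, not an improvement. What remains is inconsistency: 7.1.1 allows non-supply, 6.5 requires capture, and the SAP does not say whether an assigned zero counts as data being present.
- **Minimum-day rules.** The SAP adopts the diary assumptions and could be meant to apply the minimums to real sensor days. It does not say so, and the literal reading above leads the other way.
- **Size.** No document gives a failure rate, so nothing here shows material bias in this trial. This stands.
- **Scope.** The same measures are analysed from the diary with non-missing denominators (tables 2.34 to 2.39), the sensor tables were not strategic-interim outputs, and the primary E-RS:COPD analysis is untouched. This stands, but the diary tables do not correct the sensor tables. SAP 7.2.5 also allows further sensor analysis under a separate plan, which is optional and not available here.

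None of these points deals with a sensor that fails or is detached after randomization.

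**Conclusion.** The concern holds for sensors that stop recording after randomization: a stated rule then gives a wrong value. Recorded use can only be too low and rescue-free days too high. A reader might infer that treatment differences always shrink toward zero. That holds only if the non-recording share is equal across arms, when the factor is (1 − q); with unequal loss the bias can go either way.

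The true size cannot be computed. The illustrative 46/52/58% against 40% rests on assumed values of both p and q. The effect is confined to the sensor tables and figures of one secondary endpoint. It should be corrected because the change is small and those outputs cannot otherwise be interpreted, but it does not threaten the trial's main conclusions.

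**What to change.** Amend the sensor derivation in SAP 14.6.3:

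1. Assign 0 only on days with evidence that the sensor was active, such as a synchronisation or device-status record. Set all other days without recorded use to missing.
2. State that the 4-day baseline and 10-day monthly minimums count only valid sensor days.
3. Report sensor coverage (valid days out of possible days) by arm and month.
4. Reconcile Protocol 6.5 and 7.1.1 with SAP 5.2 and 14.6.3, so that the handling of a participant without a sensor is explicit.

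The documents do not show that an activity log exists. If there is none, keep the current rule and add a sensitivity analysis that sets to missing the periods in which the diary records rescue puffs and the sensor records none. Restricting zeros to the window between a participant's first and last sensor record should be a sensitivity analysis at most. If records are actuations, it deletes true rescue-free days in participants who stop needing rescue, and it still scores mid-period outages as zero.

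The cost is a wording change to one derivation, a coverage table, and somewhat fewer evaluable sensor days.

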**PROactive**

**General**

- A PROactive Total Score and two domain scores (amount and difficulty) are derived using data from the C-PPAC questionnaire and a physical activity monitor worn for 7 days prior to the questionnaire.
- To derive the PROactive score at each visit the following is required:
  - Response to valid (i.e., no missing items) C-PPAC questionnaire
  - Median values of steps/day and VMU/min on at least 3 days of the 7 days prior to the C-PPAC questionnaire with  $\geq 8$  hours wearing (the 3 days do not need to be consecutive).
- The C-PPAC questionnaire contains 14 items (12 questions and 2 scores from the activity monitor outputs) each scored from 0 to 4.
- The amount domain is calculated using 2 items from the C-PPAC questionnaire (amount of walking outside and chores outside) and 2 activity monitor outputs (vector magnitude units per minute (VMU/min) and steps/day).
- The difficulty domain is calculated using 10 items from the C-PPAC questionnaire.
- Each domain score is based on the addition of items (0-15 for amount and 0-40 for difficulty) and then scaled from 0-100.
- The total score is calculated as  $(\text{amount} + \text{difficulty}) / 2$
- Further details for how to score and scale the domain and total scores are outlined in the IMI PROactive user guide (14JUN16).

### 14.6.4. Safety

Adverse Events
AEs of Special Interest

 
• AEsI are defined as events in the 'Infective pneumonia' SMQ in the MedDRA version current at the time of reporting.
 
• Subjects receiving ICS (RMC - Corticosteroid – Inhaled) for at least 7 days at the time of Pneumonia onset.
 

Maximum/Minimum Post-Baseline and Worst-Case Post-Baseline
---

Definition	Reporting Details
Maximum post-baseline (QTcF, QTc B, PR interval, ECG heart rate, pulse rate, systolic BP, diastolic BP and laboratory tests)	Change from baseline of maximum value over all time-points after Day 1
Minimum post-baseline (Diastolic BP and laboratory tests that do not have a lower limit = 0)	Change from baseline of minimum value over all time-points after Day 1
Worst case post-baseline (ECG findings)	
 
• 'Abnormal' if any on-treatment assessment is evaluated as 'Abnormal'
 
• 'Unable to evaluate' if all on-treatment assessments are 'Unable to evaluate'
 
• 'Normal' if any on-treatment assessment is evaluated as 'Normal' and there are no on-treatment assessments evaluated as 'Abnormal'
 

**NOTES :**

- The treatment phase definitions specified in Section 14.4.1.4 will be used and only assessments within the on-treatment period will be considered in assessment of minimum/maximum/worst-case post-baseline.
- Assessment of minimum/maximum/worst-case post-baseline will include on-treatment data from scheduled, unscheduled and study treatment discontinuation visits (if applicable)

Laboratory Parameters
------------------------------

General
----------------

- NQ laboratory results will be treated as missing in summary displays. However, the results will be listed as received (e.g. '<x' or '>x').
- If numeric laboratory results are missing but a character result has been recorded, ie. <X, (the numeric part of the character value)/2 will be used to assign the PCI ranges.
- A 'worst case post-baseline' change classification will be derived, in which participants will be counted in the 'to low' and 'to high' categories if they reported a change from an 'in range' baseline to a value below or above the PCI criteria (respectively) at any scheduled or unscheduled on-treatment visit. Participants who did not report a change to a value outside the PCI criteria at any visit after the start of study treatment will be counted in the 'to w/in range or no change' category.

Multiple Measurements for On-Treatment Visits for Safety
---

- Participants having both high and low values relative to PCI criteria at post-baseline visits for safety parameters will be counted in both the high and low categories of the "worst case post-baseline" row of related summary tables.

ECG		
General		

 
The QTc data was collected via machine derived values (QTCB/QTCF) or manually derived values (QTCBC/QTCFC). For the purposes of reporting the following variable should be combined:                             
 
Combine QTCF with QTCFC
 
 
 
If both QTCF and QTCFC are missing (and QT and RR are non-missing then the QTcF interval will be derived as follows:                             
 
QTcF interval (msec) = <math>QT / [(RR/1000)^{(1/3)}]</math>
 
If RR interval is not collected and the corrected QT interval by Bazett's method (QTcB) is collected, then RR interval (msec) will be derived prior to deriving QTcF as follows: <math>RR \text{ interval (msec)} = 1000 * [(QT/QTcB)^2]</math>
 
 
 
If QTcF intervals are collected they will not be rederived.
 
		
ECG Categories		
Maximum and maximum increase in d QTcF values will be reported in categories as below. In subjects who have QTc above 450 at baseline, decreases that result in a QTc that remains above 450 will be considered No Change.		
ECG Parameter	Units	Category
Absolute		
Absolute QTcF Interval	msec	No Change or Decrease to $\leq 450$
		Increase To $>450$ to $\leq 480$
		Increase To $>480$ to $\leq 500$
		Increase To $>500$
Change from Baseline		
Change from Baseline QTcF	msec	Increase of $\leq 30$ ms
		Increase of 31-60 msec
		Increase of $>60$ msec

Assessment of maximum post-baseline will include on-treatment data from scheduled, unscheduled and study treatment discontinuation visits (if applicable)

